## **11.0 Criteria for Response**

The International Workshop on Chronic Lymphocytic Leukemia (IWCLL) criteria will be used. Responses will be assessed after 3, 6 and 12 cycles.

### **Assessment of Safety**

Safety assessments will consist of monitoring and recording AEs and SAEs, and should be consistent with institutional standards and Good Clinical Practice.

### **Adverse Events**

An AE is any untoward medical occurrence in a subject administered a pharmaceutical product and which does not necessarily have a causal relationship with this treatment. An

AE can therefore be any unfavorable and unintended sign (including an abnormal laboratory finding, for example), symptom, or disease temporally associated with the use of an investigational study drug, whether or not considered related to the study drug.

For the purposes of this clinical study, adverse events include only treatment-emergent events which are either new or represent detectable exacerbations of pre-existing conditions.

Adverse events may include, but are not limited to:

- Subjective or objective symptoms spontaneously offered by the subject and/or observed by the investigator or study staff including laboratory abnormalities of clinical significance.
- Any adverse events experienced by the subject through the completion of final study procedures.
- AEs not previously observed in the subject that emerge during the protocol-specified AE reporting period, including signs or symptoms associated with MCL that were not present before the AE reporting period
- Complications that occur as a result of protocol-mandated interventions (eg, invasive procedures such as biopsies)

The following are NOT considered an adverse event:

- **Pre-existing condition:** A pre-existing condition (documented on the medical history CRF) is not considered an AE unless the severity, frequency, or character of the event worsens during the study period.
- **Preplanned hospitalization:** A hospitalization planned before signing the informed consent form is not considered an SAE, but rather a therapeutic intervention. However, if during the pre-planned hospitalization an event occurs, which prolongs the hospitalization or meets any other SAE criteria, the event will be considered an SAE. Surgeries or interventions that were under consideration but not performed before enrollment in the study will not be considered serious if they are performed after enrollment in the study for a condition that has not changed from its baseline level. Hospitalizations for social reasons or due to long travel distances are also not SAEs.
- **Diagnostic Testing and Procedures:** Testing and procedures should not to be reported as adverse events or serious adverse events, but rather the cause for the test or procedure should be reported.

### **Suspected Adverse Reaction**

A Suspected Adverse Reaction is any adverse event for which there is a “reasonable possibility” that the drug caused the adverse event.

“Reasonable Possibility”, for the purposes of safety reporting, means there is evidence to suggest a causal relationship between the drug and the adverse event. Examples of evidence that would suggest a causal relationship between the drug and the adverse event are:

- A single occurrence of an event that is uncommon and known to be strongly associated with drug exposure (eg, angioedema, blood dyscrasias, rhabdomyolysis, hepatic injury, anaphylaxis, and Stevens-Johnson Syndrome).
- One or more occurrences of an event that is not commonly associated with drug exposure, but is otherwise uncommon in the population exposed to the drug (eg, include tendon rupture or heart valve lesions in young adults, or intussusception in healthy infants). If the event occurs in association with other factors strongly suggesting causation (eg, strong temporal association, event recurs on rechallenge), a single case may be sufficiently persuasive; but often, more than one occurrence (from one or multiple studies) would be needed before the sponsor could make a determination of whether the drug caused the event.
- An aggregate analysis of specific events that can be anticipated to occur in the study population independent of drug exposure. Such events include known consequences of the underlying disease or condition under investigation (eg, symptoms or disease progression), or events unlikely to be related to the underlying disease or condition under investigation, but commonly occur in the study population independent of drug therapy (eg, cardiovascular events in an elderly population). An aggregate analysis (across studies) will identify those events that occur more frequently in the drug treatment group than in a concurrent or historical control group.

### **Severity**

Definitions found in the Common Terminology Criteria for Adverse Events version 4.0 (CTCAE v4.0) will be used for grading the severity (intensity) of AEs. The CTCAE v4.0 displays Grades 1 through 5 with unique clinical descriptions of severity for each referenced AE. Should a patient experience any AE not listed in the CTCAE v4.0, the following grading system should be used to assess severity:

- Grade 1 (Mild AE) – experiences which are usually transient, requiring no special treatment, and not interfering with the patient’s daily activities
- Grade 2 (Moderate AE) – experiences which introduce some level of inconvenience or concern to the patient, and which may interfere with daily activities, but are usually ameliorated by simple therapeutic measures
- Grade 3 (Severe AE) – experiences which are unacceptable or intolerable, significantly interrupt the patient’s usual daily activity, and require systemic drug therapy or other treatment

- Grade 4 (Life-threatening or disabling AE) – experiences which cause the patient to be in imminent danger of death
- Grade 5 (Death related to AE) – experiences which result in patient death

### **Causality**

The investigator is to assess the causal relation (ie, whether there is a reasonable possibility that the study drug caused the event).

### **Unexpected**

An “unexpected” AE is an AE that is not listed in the Investigator Brochure or is not listed at the specificity or severity that has been observed. For example, hepatic necrosis would be “unexpected” (by virtue of greater severity) if the Investigator Brochure referred only to elevated hepatic enzymes or hepatitis. Similarly, cerebral thromboembolism and cerebral vasculitis would be “unexpected” (by virtue of greater specificity) if the Investigator Brochure listed only cerebral vascular accidents. "Unexpected" also refers to AEs that are mentioned in the Investigator Brochure as occurring with a class of drugs or as anticipated from the pharmacological properties of the drug, but are not specifically mentioned as occurring with the study drug under investigation.

### **Serious Adverse Event Reporting (SAE) for MD Anderson sponsored IND Protocols**

An adverse event or suspected adverse reaction is considered “serious” if, in the view of either the investigator or the sponsor, it results in any of the following outcomes:

- Death
- A life-threatening adverse drug experience – any adverse experience that places the patient, in the view of the initial reporter, at immediate risk of death from the adverse experience as it occurred. It does not include an adverse experience that, had it occurred in a more severe form, might have caused death.
- Inpatient hospitalization or prolongation of existing hospitalization.
- A persistent or significant incapacity or substantial disruption of the ability to conduct normal life functions.
- A congenital anomaly/birth defect.

Important medical events that may not result in death, be life-threatening, or require hospitalization may be considered a serious adverse drug experience when, based upon appropriate medical judgment, they may jeopardize the patient or subject and may require medical or surgical intervention to prevent one of the outcomes listed in this definition. Examples of such medical events include allergic bronchospasm requiring intensive treatment in an emergency room or at home, blood dyscrasias or convulsions that do not result in inpatient hospitalization, or the development of drug dependency or drug abuse (21 CFR 312.32).

- Important medical events as defined above, may also be considered serious adverse events. Any important medical event can and should be reported as an SAE if deemed appropriate by the Principal Investigator or the IND Sponsor, IND Office.
- All events occurring during the conduct of a protocol and meeting the definition of a SAE must be reported to the IRB in accordance with the timeframes and procedures outlined in “The University of Texas M. D. Anderson Cancer Center Institutional Review Board Policy for Investigators on Reporting Unanticipated Adverse Events for Drugs and Devices”. Unless stated otherwise in the protocol, all SAEs, expected or unexpected, must be reported to the IND Office, regardless of attribution (within 5 working days of knowledge of the event).
- **All life-threatening or fatal events**, that are unexpected, and related to the study drug, must have a written report submitted within **24 hours** (next working day) of knowledge of the event to the Safety Project Manager in the IND Office.
- Unless otherwise noted, the electronic SAE application (eSAE) will be utilized for safety reporting to the IND Office and MDACC IRB.
- Serious adverse events will be captured from the time of the first protocol-specific intervention, until 30 days after the last dose of drug, unless the participant withdraws consent. Serious adverse events must be followed until clinical recovery is complete and laboratory tests have returned to baseline, progression of the event has stabilized, or there has been acceptable resolution of the event.
- Additionally, any serious adverse events that occur after the 30 day time period that are related to the study treatment must be reported to the IND Office. This may include the development of a secondary malignancy.

### **Reporting to FDA**

Serious adverse events will be forwarded to FDA by the IND Sponsor (Safety Project Manager IND Office) according to 21 CFR 312.32.

**It is the responsibility of the PI and the research team to ensure serious adverse events are reported according to the Code of Federal Regulations, Good Clinical Practices, the protocol guidelines, the sponsor’s guidelines, and Institutional Review Board policy.**

### **Protocol-specific dose adjustments**

#### **PCI-32765 dose adjustments for surgical or invasive procedures:**

The following guidance should be applied during the perioperative period for subjects who require surgical intervention or an invasive procedure while receiving ibrutinib:

- For any surgery or invasive procedure requiring sutures or staples for closure, Ibrutinib should be held at least 7 days prior to the intervention and should be held at least 7 days after the procedure, and restarted at the discretion of the investigator when the surgical site is reasonably healed without serosanguineous drainage or the need for drainage tubes.

- For minor procedures (such as a central line placement, needle biopsy, thoracentesis, or paracentesis) ibrutinib should be held for at least 3 days prior to the procedure and should not be restarted for at least 3 days after the procedure. For bone marrow biopsies that are performed while the subject is on ibrutinib, it is not necessary to hold ibrutinib for these procedures.
- For emergency procedures, ibrutinib should be held after the procedure until the surgical site is reasonably healed, for at least 7 days after the urgent surgical procedure.

**PCI-32765 dose adjustments for the following hematologic toxicities:**

- Grade 4 ANC (< 500/ $\mu$ L) for > 7 days
- Grade 3 or 4 Platelets (< 50,000/ $\mu$ L) in presence of significant bleeding
- Grade 4 Platelets (< 25,000/ $\mu$ L)

Gastrointestinal toxicities:

- Grade 3 or 4 nausea, vomiting or diarrhea if persistent despite optimal antiemetic and/or anti-diarrheal therapy) or any other grade 4 or unmanageable grade 3 toxicities:

Occurrence	Action
1 st	Hold PCI-32765 until recovery to Grade $\leq$ 1 or baseline; may restart at original dose level
2 nd	Hold PCI-32765 until recovery to Grade $\leq$ 1 or baseline; restart at one dose level lower (280 mg daily)
3 rd	Hold PCI-32765 until recovery to Grade $\leq$ 1 or baseline; restart at one dose level lower (140 mg daily)
4 th	Discontinue PCI-32765

**Events of Special Interest**

Specific adverse events, or groups of adverse events, will be followed as part of standard safety monitoring activities by the Sponsor. These events will be reported to the Pharmacovigilance within 24 hours of awareness following the procedure described for SAEs and will require enhanced data collection. All Events of Special Interest will be submitted without a serious criterion selected if no other serious criterion is met.

**List of Events of Special Interest**

**Major Hemorrhage**

Defined as any hemorrhagic event, that is Grade 3 or greater in severity, or that results in one of the following: intraocular bleeding causing loss of vision, the need for a transfusion of two or more units of red cells or an equivalent amount of whole blood, hospitalization or prolongation of hospitalization.

Events meeting the definition of major hemorrhage will be captured as an event of special interest (see above).

## **DOCUMENTING AND REPORTING OF ADVERSE AND SERIOUS ADVERSE EVENTS**

The investigator is responsible for ensuring that all AEs and SAEs that are observed are reported during the study.

### **Adverse Event Reporting Period**

The AE reporting period for this study begins when the patient takes the first dose of study drug and ends with the safety follow-up visit. If an SAE is present at the safety follow-up visit, or within 30 days of the last dose of study drug (whichever is later), the SAE (and associated AEs and concomitant medications) should be followed to resolution or until the Investigator assesses the subject as stable, or the subject is lost to follow-up or withdraws consent. Resolution/stable means the subject has returned to baseline state of health or the investigator does not expect any further improvement or worsening of the event.

### **Assessment of Adverse Events**

Investigators will assess the occurrence of AEs and SAEs at all patient evaluation time points during the study. All AEs and SAEs whether volunteered by the patient, discovered by study personnel during questioning, or detected through physical examination, clinically significant laboratory test, or other means will be recorded in the patient's medical record and on the CRF and, when applicable, on an SAE form.

Each recorded AE or SAE will be described by its duration (ie, start and end dates), severity, regulatory seriousness criteria, if applicable, suspected relationship to the investigational product (see following guidance), and any actions taken.

All SAEs (initial and follow-up information) will be reported by the investigator, or designee, to Pharmacyclics, within 24 hours, or the next business day, after discovery of the event or information. The sponsor and Pharmacyclics may request follow-up and other additional information (eg, hospital admission/discharge notes, and laboratory results).

All deaths should be reported with the primary cause of death as the AE term, as death is typically the outcome of the event, not the event itself. The primary cause of death on the autopsy report should be the term reported.

An SAE will qualify for expedited reporting to regulatory authorities if the SAE is considered a Suspected Adverse Reaction and is not listed in the current Investigator's Brochure (ie, an unexpected event).

To ensure consistency of AE and SAE causality assessments, investigators should apply the following general guideline:

- Fatal: Adverse event resulted in death.
- Unrelated: Another cause of the adverse event is more plausible; a temporal sequence cannot be established with the onset of the adverse event and administration of the investigational product; or, a causal relationship is considered biologically implausible.
- Possibly Related: There is a clinically plausible time sequence between onset of the adverse event and administration of the investigational product, but the adverse event could also be attributed to concurrent or underlying disease, or the use of other drugs or procedures. Possibly related should be used when the investigational product is one of several biologically plausible adverse event causes.
- Definitely Related: The adverse event is clearly related to use of the investigational product.

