
drug by the investigator. These were one case of viral lymphadenitis, one case of a subdural hematoma, one case of viral infection (follow-up reported as unrelated), one case of decreased appetite, dehydration, and asthenia, one case of sepsis, and one case of headache and dizziness (follow-up reported as unrelated viral vestibular neuritis) and one case of hemorrhagic colitis. Two subjects in this pooled analysis died from progressive disease. Diarrhea, nausea, and fatigue have been the most commonly reported AEs; with most of these occurring early in treatment (cycles 1 or 2). Significant myelosuppression has been infrequent; with grade 3 or greater thrombocytopenia or neutropenia reported in less than 5% of subjects. Significant hepatic or renal toxicity has been absent. In addition, with longer-term follow-up, there has been no evidence of cumulative toxicity, either overall or related to specific events. Because of the controversial role of Btk in platelet function and aggregation, subjects with a history of bleeding diathesis or coagulopathy, recent surgical procedure, stroke, or hemorrhage, and subjects receiving Coumadin will be excluded.

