Bone marrow aspiration and biopsy will be obtained within one month of day 1 of the study, and again after 3, 6, and 12 cycles (+/- 1 month), only bone marrow aspirations (no biopsy) will be done during follow-up evaluations after 3, 6, and 12 cycles) after initiating PCI-32765 therapy. The screening bone marrow will be evaluated by flow cytometry for clonality and for *IGHV* mutation studies (unless known), CD38 expression, ZAP-70 expression, and cytogenetic and genomic abnormalities by FISH. Follow-up bone marrow tests after 3, 6, and 12 cycles (+/- 1 month) will evaluate morphology (bone marrow lymphocyte quantification), and quantification of CLL cells by flow cytometry, including minimal residual disease assessment by flow cytometry. Electrocardiogram (within one month from registration) will be required. We will not require additional ECG monitoring during this study. As of April 6, 2012, 408 subjects have been treated with ibrutinib in 8 clinical studies. The cardiovascular safety of ibrutinib was evaluated by monitoring of adverse events in all studies; in addition, a formal ECG monitoring was performed in 2 studies (PCYC-04753 & PCYC-1102-CA). To date there is no evidence of ECG morphological changes or prolongation of QTc in patients treated with ibrutinib. The most common cardiovascular adverse events reported across the studies were atrial fibrillation (n=17), tachycardia (n=7), sinus tachycardia (n=4) and sinus bradycardia (n=3). Events of Grade 3 or greater severity included only atrial fibrillation (n=6), supraventricular tachycardia (n=2) and tachycardia (n=1). These findings are consistent with expectations in elderly population of subjects many of whom have known cardiovascular disease at baseline. Because of these data we will not request follow-up ECGs. Subjects also will undergo CT scans of the chest, abdomen, and pelvis after 3 or 6 cycles (+/- 1 month) and after 12 cycles (+/- 1 month) of PCI-32765 therapy. Anti-coagulated blood sample (50ml) and coagulated blood sample (10ml) for baseline H2O studies on the day of study initiation (Day 1).

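### The causality guideline lets an event be coded *Unrelated* merely because another cause is likelier, which overlaps *Possibly Related* and departs from the protocol's own reasonable-possibility test

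*Combined protocol and SAP*

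**What the plan says.** The guideline under Assessment of Adverse Events has four entries: *Fatal* (an outcome rather than a causality grade), *Unrelated*, *Possibly Related* and *Definitely Related*.

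- *Unrelated* begins "Unrelated: Another cause of the adverse event is more plausible". Two further grounds follow: no temporal sequence can be established, or a causal link is biologically implausible. The three are joined by 'or'.
- *Possibly Related* requires plausible timing, "but the adverse event could also be attributed to concurrent or underlying disease, or the use of other drugs or procedures". Its instruction on use is: "Possibly related should be used when the investigational product is one of several biologically plausible adverse event causes".

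Two other sections set the causality standard. Causality asks the investigator to judge "whether there is a reasonable possibility that the study drug caused the event". Suspected Adverse Reaction explains that a reasonable possibility "means there is evidence to suggest a causal relationship between the drug and the adverse event".

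The link to reporting is also under Assessment of Adverse Events: "An SAE will qualify for expedited reporting to regulatory authorities if the SAE is considered a Suspected Adverse Reaction". The sentence goes on to require that the event be absent from the current Investigator's Brochure.

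**The concern.** The first ground of *Unrelated* is comparative: it asks whether some other cause is likelier than the drug. The Causality and Suspected Adverse Reaction sections apply a threshold instead: is there evidence pointing to the drug? An event can pass that threshold while another cause is still judged likelier. The guideline then supports two opposite codes, although its stated purpose is consistent assessment.

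The code matters because several reporting duties turn on relatedness or on suspected-reaction status. The ambiguity has consequences mainly in one direction: an event for which the drug is a plausible cause can be moved to *Unrelated* and so fall outside those duties.

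**Working it through.** The plan gives no figure to reproduce, so the check is a comparison of definitions on one test case.

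**Test case.** A life-threatening event, not listed in the Investigator's Brochure, with plausible timing and some evidence implicating the drug, where the investigator thinks underlying CLL is the likelier explanation.

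**Step 1: apply each definition.**

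| Rule | Test | Result |
|---|---|---|
| Suspected Adverse Reaction; Causality | Evidence suggesting the drug caused it? | Yes: suspected reaction |
| *Possibly Related* | Plausible timing, drug among several plausible causes? | Yes |
| *Unrelated*, first ground | Another cause more plausible? | Yes |

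The event meets both codes.

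**Step 2: look for a tie-break.** The guideline states no precedence. No section says which of its entries amount to a Suspected Adverse Reaction.

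**Step 3: follow an *Unrelated* code through the reporting rules.**

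- *24-hour IND Office report* (Serious Adverse Event Reporting section). It applies to unexpected fatal or life-threatening events that are related. The condition fails, so the report is not triggered. This effect is direct.
- *Serious events more than 30 days after the last dose* (same section). These must go to the IND Office only if related. An *Unrelated* code removes the duty. This effect is also direct.
- *7- and 15-day notifications* (Assessment of Adverse Events; Expedited Reporting Requirements). The trigger is suspected-reaction status plus unexpectedness. An *Unrelated* code would probably be taken to mean that the event is not a suspected reaction. This is an inference, because the documents contain no mapping.

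**Step 4: list what does not depend on the code.**

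- All serious events in the capture period go to the IND Office within 5 working days, whatever the attribution. They also go to the IRB under institutional policy.
- All serious events go to the drug supplier within 24 hours or the next business day.
- Major hemorrhage, as an event of special interest, is reported within 24 hours with no relatedness condition.
- The Section 13.0 stopping rule (more than 30% of patients with grade 3-4 non-hematological toxicity) does not mention attribution.

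**Step 5: size of the direct delay.** The 24-hour report is glossed as the next working day, taken here as 1 working day. The general limit is 5 working days. For the test case, the latest permitted arrival at the IND Office moves by 5 − 1 = 4 working days. The drug supplier's deadline does not move. For a serious event after 30 days, the explicit duty to report to the IND Office disappears.

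**The case against.** The strongest reply is that the safety net does not rest on this code. Expedited reporting is triggered by suspected-reaction status, which has its own definition, and the Causality section puts that same question to the investigator. The IND Office and the drug supplier see every serious event in the capture period. Reporting to FDA has the IND sponsor forwarding serious events, and the Suspected Adverse Reaction section contemplates a sponsor's own judgement on causality. The *Possibly Related* instruction already covers the case of several plausible causes without ranking them, so it can be read as governing.

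Much of this stands, and it limits the consequence to events that may not be expedited. It does not remove the contradiction. An investigator who starts from the *Unrelated* entry is following the text just as faithfully. No section requires a second causality assessment on receipt, and the Expedited Reporting Requirements place the notification on the investigator, who also applies this guideline. After 30 days, the IND Office duty itself depends on relatedness.

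Three stronger readings are tempting, and the documents do not support them:

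- *That Section 2.5 shows how far coding shifts.* It mentions "one case of viral infection (follow-up reported as unrelated" and a second such change. But it counts fourteen subjects with a serious event and, separately, seven related events, so no proportion can be formed. It also does not show that wording like this guideline's caused either change.
- *That atrial fibrillation would be coded away.* Section 7.0 says of cardiovascular events, "These findings are consistent with expectations in elderly population of subjects many of whom have known cardiovascular disease at baseline". That is background for omitting follow-up ECGs and assigns causality to no case.
- *That a related-event rate would be biased downward.* Section 13.0 plans no analysis by relatedness.

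**Conclusion.** The point holds as a conflict between definitions with a bounded effect on reporting. A suspected reaction can be coded *Unrelated* under the guideline's own words. Two reporting rules are directly exposed: the 24-hour IND Office report, with up to 4 working days' later arrival permitted, and the report of serious events after 30 days, where the duty lapses. The 7- and 15-day notifications are exposed only by inference, on the assumption that *Unrelated* would be read as not a suspected reaction.

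A reader might infer that such events, including bleeding, would be hidden. The documents do not support that: serious events in the capture period are still transmitted, and major hemorrhage has its own route. How often the overlap would arise cannot be estimated from the documents. The change is worth making because the protocol already contains the standard needed to resolve the conflict.

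**What to change.** In the causality guideline under Assessment of Adverse Events:

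1. Replace the first ground of *Unrelated* with: 'there is no reasonable possibility that the product caused the event'. Keep the temporal and implausibility grounds.
2. Add: 'If the product is one of several plausible causes, code Possibly Related even when another cause is judged more likely.'
3. State that *Possibly Related* and *Definitely Related* both count as a Suspected Adverse Reaction as defined in that section.

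The cost is a few sentences of text, with no new data, visits or procedures. The downside is that a few more events may be coded related and a few more expedited reports filed.
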